7.2.3 Diabetes Mellitus

Type 1 diabetes mellitus (if new onset, including diabetic ketoacidosis [DKA]) or **Grade 3-4 Hyperglycemia**, if associated with ketosis (ketonuria) or metabolic acidosis (DKA)

- Insulin replacement therapy is recommended for Type 1 diabetes mellitus and for Grade 3-4 hyperglycemia associated with metabolic acidosis or ketonuria.
- Evaluate patients with serum glucose and a metabolic panel, urine ketones, glycosylated hemoglobin, and C-peptide.

7.2.4 Hypophysitis

- For **Grade 2** events, treat with corticosteroids. When symptoms improve to Grade 1 or less, steroid taper should be started and continued over no less than 4 weeks. Replacement of appropriate hormones may be required as the steroid dose is tapered.
- For **Grade 3-4** events, treat with an initial dose of IV corticosteroids followed by oral corticosteroids. When symptoms improve to Grade 1 or less, steroid taper should be started and continued over no less than 4 weeks. Replacement of appropriate hormones may be required as the steroid dose is tapered.

7.2.5 Hyperthyroidism or Hypothyroidism

Thyroid disorders can occur at any time during treatment. Monitor patients for changes in thyroid function (at the start of treatment, periodically during treatment, and as indicated based on clinical evaluation) and for clinical signs and symptoms of thyroid disorders.

- **Grade 2** hyperthyroidism events (and **Grade 2-4** hypothyroidism):
 - In hyperthyroidism, non-selective beta-blockers (e.g. propranolol) are suggested as initial therapy.
 - In hypothyroidism, thyroid hormone replacement therapy, with levothyroxine or liothyroinine, is indicated per standard of care.
- **Grade 3-4** hyperthyroidism
 - Treat with an initial dose of IV corticosteroid followed by oral corticosteroids. When symptoms improve to Grade 1 or less, steroid taper should be started and continued over no less than 4 weeks. Replacement of appropriate hormones may be required as the steroid dose is tapered.

7.2.6 Hepatic

- For **Grade 2** events, monitor liver function tests more frequently until returned to baseline values (consider weekly).
 - Treat with IV or oral corticosteroids
- For **Grade 3-4** events, treat with intravenous corticosteroids for 24 to 48 hours.

- When symptoms improve to Grade 1 or less, a steroid taper should be started and continued over no less than 4 weeks.

7.2.7 Renal Failure or Nephritis

- For **Grade 2** events, treat with corticosteroids.
- For **Grade 3-4** events, treat with systemic corticosteroids.
- When symptoms improve to Grade 1 or less, steroid taper should be started and continued over no less than 4 weeks.

7.2.8 Infusion Reactions

Signs and symptoms usually develop during or shortly after drug infusion and generally resolve completely within 24 hours of completion of infusion. Appropriate resuscitation equipment should be available in the room and a physician readily available during the period of drug administration.

Table 7.2.8 below shows treatment guidelines for subjects who experience an infusion reaction associated with administration of pembrolizumab.

Table 7.2.8 Infusion Reaction Treatment Guidelines

NCI-CTCAE Grade	Treatment	Premedication at Subsequent Dosing
Grade 1 Mild reaction; infusion interruption not indicated; intervention not indicated	Increase monitoring of vital signs as medically indicated until the subject is deemed medically stable in the opinion of the investigator.	None

NCI-CTCAE Grade	Treatment	Premedication at Subsequent Dosing

Grade 2 Requires infusion interruption but responds promptly to symptomatic treatment (e.g., antihistamines, NSAIDS, narcotics, IV fluids); prophylactic medications indicated for <=24 hrs
	
Stop Infusion and monitor symptoms. Additional appropriate medical therapy may include but is not limited to:
 
 • IV fluids • Antihistamines • NSAIDS • Acetaminophen • Narcotics 
Increase monitoring of vital signs as medically indicated until the subject is deemed medically stable in the opinion of the investigator.
 
If symptoms resolve within 1hr of stopping drug infusion, the infusion may be restarted at 50% of the original infusion rate (e.g., from 100 mL/hr to 50 mL/hr). Otherwise dosing will be held until symptoms resolve and the subject should be premedicated for the next scheduled dose.
 
Subjects who develop Grade 2 toxicity despite adequate premedication should be permanently discontinued from further trial treatment administration.
	
Subject may be premedicated 1.5hr (\pm 30 minutes) prior to infusion of pembrolizumab with:
 
 • Diphenhydramine 50 mg po (or equivalent dose of antihistamine). • Acetaminophen 500-1000 mg po (or equivalent dose of antipyretic).

Grades 3 or 4
 
Grade 3: Prolonged (i.e., not rapidly responsive to symptomatic medication and/or brief interruption of infusion); recurrence of symptoms following initial improvement; hospitalization indicated for other clinical sequelae (e.g., renal impairment, pulmonary infiltrates)
 
Grade 4: Life-threatening; pressor or ventilatory support indicated
	
Stop Infusion. Additional appropriate medical therapy may include but is not limited to:
 
 • IV fluids • Antihistamines • NSAIDS • Acetaminophen • Narcotics • Oxygen • Pressors • Corticosteroids • Epinephrine 
Increase monitoring of vital signs as medically indicated until the subject is deemed medically stable in the opinion of the investigator.
 
Hospitalization may be indicated.
 
Subject is permanently discontinued from further trial treatment administration.
	
No subsequent dosing

8.0 CORRELATIVES

Tissue and blood based biomarker studies will be performed to better understand the role of factors that may be associated with efficacy or toxicity from study treatment and/or cancer biology. Additional markers related to efficacy, toxicity, and/or cancer biology may be analyzed. Anticipated analyses are listed below and focus on factors associated with angiogenesis, inflammation, immunity, and tumor growth. However, final analyte lists and technology platforms will be based upon best science and available funding at the time of analysis. External vendors and collaborators may conduct or participate in these analyses, provided samples are de-identified. All collaborations will be subject to Duke policies on sample and data sharing.

8.1 Tumor Tissue Biomarkers

Archived formalin fixed paraffin embedded (FFPE) tumor tissue will be collected for all subjects (if available). Refer to *Study Manual* for collection, processing, and submission details.

For patients accrued to the dose expansion cohort, pre-treatment and on-treatment tumor biopsies will be performed only on patients who have a tumor lesion that is amenable to safe biopsy. In the biomarker cycle, patients will undergo tumor biopsy up to 1 week before starting treatment (i.e., pre-treatment) and will undergo a second tumor biopsy on Day 7 or 8 prior to start of oxaliplatin and capecitabine (i.e., on-treatment). The preferred type of biopsy is a core biopsy: five 18-gauge core needle biopsies (diameter about 2 mm) with a throw length of approximately 2 cm will provide adequate tissue for study. Refer to *Study Manual* for collection, processing, and submission details. Note: Those patients accrued to the dose expansion cohort who do not have a tumor lesion that is amenable to safe biopsy will only have blood-based biomarker collections in the biomarker cycle (ie. Cycle 1).

We will interrogate these tissue specimens using whole exomic sequencing studies, spatial transcriptomic analysis, and proximity ligation assays to spatially resolve the impact of pembrolizumab on tumor T cell/PMN-MDSC infiltration and NLRP3 inflammasome activation. These data will be correlated with mutations associated with this resistance pathway as well as with clinical response. This work will leverage a rare tissue bank of pre- and post-pembro tumor specimens to reveal a series of novel pharmacologic targets and potential biomarkers capable of overcoming immunotherapy resistance and improving the management of patients with gastrointestinal malignancies.

Archived FFPE tumor tissue and pre-treatment/on-treatment tumor biopsy samples will be tested by IHC for CD8 and PDL1 staining, the primary biomarker endpoints for this study. Expression of additional proteins that may be associated with sensitivity or resistance to pembrolizumab or XELOX and pembrolizumab, including but, not limited to, TGF β 1, STAT3, and various immune cell populations, including CD3, CD4, CD8, Treg, (FoxP3), Th17 T-cells and monocyte/macrophage and neutrophil populations. RNA Seq or PCR may also be performed for analyses of factors that may be associated with sensitivity or resistance to these agents including but not limited to CD3, CD4, CD8, EOMES, IFN γ , FOXP-3, Granzyme-A, Granzyme-B, Perforin, IL1 β , IL6, IL7, IL10, IL11, IL12, IL17A, IL17E, IL22, and IL23. Micro-satellite instability (MSI) by IHC and/or polymerase chain reaction (PCR) may also be assessed.

Genetic alterations, including both gene mutation and copy number alteration, may be characterized using a customized Next Gen Sequencing platform. Samples evaluated will be archived FFPE tumor samples. Further refinement of these approaches can be made depending on interest.

8.2 Circulating Immune Cells (PBMC)

Peripheral blood will be collected for peripheral blood mononuclear cells (PBMCs) from each subject at the following timepoints: baseline, end of monotherapy lead-in on Day 8 (biomarker cycle of dose

expansion cohort only), end of first cycle of combination therapy on Day 29 (biomarker cycle of dose expansion cohort only), first restaging only, disease progression or treatment discontinuation, and for complete responders on long term follow-up. Refer to *Study Manual* for collection and submission details.

PBMCs will be processed and stored by the Duke Immune Profiling Core facility under the direction of [name]. Polychromatic flow cytometry (PFC) panels will be used to compare treatment related changes in both tumor and peripheral immune cell compartments. Up to 50 markers may be analyzed using 3 PFC panels: 1) a 12-color 'Exhaustion Panel', 2) a 12-color 'Tumor Reactive T Cell Panel', and 3) a 14-color regulatory T cell (Treg) and myeloid-derived suppressor cells (MDSC) panel. This analysis will be overseen by [name].

8.3 Protein Multiplex Arrays (Plasma)

Peripheral blood will be collected for plasma from each subject at the following timepoints: baseline, end of monotherapy lead-in on Day 8 (biomarker cycle of dose expansion cohort only), end of first cycle of combination therapy on Day 29 (biomarker cycle of dose expansion cohort only), every restaging, disease progression or treatment discontinuation, off treatment follow-up, and for complete responders on long term follow-up. Refer to *Study Manual* for collection, processing, and submission details.

Plasma will be stored by the Duke Phase I Biomarker Laboratory under the direction of [name]. Markers of inflammation will be analyzed in the Duke Phase I Biomarker lab. Analyses will be performed on pre-treatment and on-treatment samples. Analyte levels, and changes in analyte levels, will be correlated with clinical outcome (PFS, OS). Plasma and serum samples will be evaluated by ELISA for protein markers that may be associated with sensitivity or resistance to pembrolizumab. These may include CRP and other markers of inflammation, including but not limited to IFNy, IL1 β , IL4, IL6, IL7, IL10, IL12, IL17A, IL17E, and IL23.

8.4 Pharmacogenomics (Whole Blood)

Subjects will have whole blood collected at baseline. Refer to *Study Manual* for collection, processing, and submission details.

Whole blood will be stored for possible future analysis of HLA type and other candidate markers of efficacy and toxicity by the Duke Phase I Biomarker Laboratory under the direction of [name] with the consent of the patient.

8.5 Future Use of Patient Samples

Any remaining biological materials at the end of the study will be deidentified and deidentified samples may be retained for possible use in biomarker research with the consent of the patient.

8.6 Correlative Collaborations

8.6.1. Duke-Personalis Collaboration

In order to identify potential mechanisms of sensitivity and resistance to pembrolizumab in gastric cancer and to better characterize the changes of key tumor and immune factors in response to pembrolizumab therapy, we plan to collaborate with Personalis, Inc. for both tissue- and blood-based biomarker analyses using their comprehensive, state-of-the-art technology platforms (<https://www.personalis.com/>).

8.6.1.1 The following samples for the specified assays and analytic pipelines will be shared with Personalis.

Sample Type	Sample Format/Quantity	Assay Type
FFPE tumor tissue 50 samples	4 x 5um unstained slides or 2 x 10um curls, 25mm ² surface area per sample	ImmunolID NeXT
PBMC 36 samples	2-4 million frozen PBMC per sample	ImmunolID NeXT
Plasma 150 samples	Up to 8 ml per sample	NeXT Liquid Biopsy

8.6.1.2 The following clinical data will be shared with Personalis in order to utilize pre-existing biomarker analytic pipelines. Duke statisticians will work with both teams in a collaborative fashion to analyze and interpret the data from each project.

- Deidentified patient metadata.
 - Patient age, gender, race/ethnicity, prior therapies, treatment duration, treatment dosage, smoking status, tumor size, tumor site
- RECIST and iRECIST response data for each patient case per timepoint
- Deidentified patient outcomes data.
 - OS, PFS and response to therapy

No personal health information will be shared with Personalis.

8.6.2 Duke – Olink Collaboration

In order to identify potential mechanisms of sensitivity and resistance to pembrolizumab in gastric cancer and to better characterize the changes of key tumor and immune factors in response to pembrolizumab therapy, we plan to collaborate with Olink for both tissue- and blood-based biomarker analyses using their comprehensive, state-of-the-art technology platforms (<https://www.olink.com/>)

8.6.2.1 The following samples for the specified assays and analytic pipelines will be shared with Olink.

Sample Type	Sample Format/Quantity	Assay Type
Fresh frozen tumor tissue 25 samples	Tissue lysate, 20 ug per sample	Olink Explore 1536
PBMC 150 samples	Cell lysate, 1000 PBMCs per sample	Olink Explore 1536
Plasma 150 samples	100 µl per sample	Olink Explore 1536

8.6.2.2 The following clinical data will be shared with Olink in order to utilize pre-existing biomarker analytic pipelines. Duke statisticians will work with both teams in a collaborative fashion to analyze and interpret the data from each project.

- Deidentified patient metadata.
 - Patient age, gender, race/ethnicity, prior therapies, treatment duration, treatment dosage, smoking status, tumor size, tumor site
- RECIST and iRECIST response data for each patient case per timepoint
- Deidentified patient outcomes data.
 - OS, PFS and response to therapy

No personal health information will be shared with Olink.

9.0 STATISTICAL ANALYSIS

9.1 General Analysis Considerations

Thirty-five (35) evaluable patients will be enrolled and treated.

9.1.1 Primary Endpoint

The primary endpoint will be progression-free survival (PFS) measured from study entry until documented progression or death from any cause. Patients who have not experienced progression will be censored at the date of the last radiographic assessment. Based on the results of the AVAGAST and ToGA trials a median PFS of approximately 5.5 months is expected for patients treated with oxaliplatin and capecitabine alone. Also, observed PFS hazard ratios of 0.80 and 0.71 were reported for AVAGAST and ToGA, respectively. With 35 patients enrolled, the difference between a historical median PFS of 5.5 months and experimental median of 7.3 months, a hazard ratio of 0.75, can be detected with 80% power (1-sided test of single exponential mean, $\alpha=0.2$).

PFS and median PFS will be estimated using the Kaplan-Meier method. The 95% confidence interval estimate for median PFS will be computed using the variance estimate proposed by Brookmeyer and Crowley. Under the alternative hypothesis, 32 PFS events are expected at the end of the follow-up period.

The primary analysis of PFS will be intention-to-treat in that all patients who have undergone at least one scheduled restaging on-treatment, or who have had unequivocal progression prior to the first scheduled restaging will be followed for progression. These patients will be followed for PFS, even if they are removed from treatment due to unacceptable toxicity or because they withdrew consent. As a secondary analysis, these patients will be censored at the time they were removed from treatment.

The magnitude of reduction in tumor burden will be summarized descriptively (such as a waterfall plot) based on change in the sum of the longest diameters of target lesions relative to baseline.

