5.7 Subject Discontinuation

Subjects will receive study treatment until treatment discontinuation for one of the reasons listed below. However, subjects may discontinue study treatment or withdraw their consent to participate in the study at any time without prejudice. All reasons for discontinuation or withdrawal from trial will be recorded.

The maximum duration of treatment for pembrolizumab will be up to 35 cycles. The duration of treatment for XELOX will be until unacceptable drug-related toxicity or disease progression. If capecitabine is not tolerated, monotherapy with pembrolizumab may be continued. Patients who complete 35 cycles of therapy and have complete response or prolonged stable disease may also elect to end therapy with capecitabine after a discussion with their treating physician and with approval of the PI. Re-introduction of oxaliplatin is permitted provided that neuropathy has improved. Reasons for subject discontinuation by the Investigator may include, but are not limited to, the following:

- Death
- Confirmed radiographic disease progression (Note: With approval of the Lead PI, a subject may be granted an exception to continue on study treatment with confirmed radiographic progression if clinically stable or clinically improved.)
- Significant noncompliance by subject or Investigator
- Investigator or Lead PI determination that it is no longer safe and/or no longer in the subject's best interest to continue participation
- Withdrawal of consent
- Lost to follow-up
- Necessity for treatment with other anticancer treatment prohibited by protocol
- Sexually active subjects who refuse to use medically accepted methods of contraception during the course of the study and for 120 days following the last dose of study drug
- Women who become pregnant or are breast feeding
- Request by regulatory agencies for termination of treatment of an individual subject or all subjects under the protocol
- The following **Treatment-Related Discontinuation Criteria** attributed to pembrolizumab:
 - Any Grade 2 uveitis, eye pain, or blurred vision that does not respond to topical therapy and does not improve to Grade 1 OR requires systemic treatment.
 - Recurrent Grade 2 pneumonitis
 - Any Grade 3 non-skin adverse event lasting > 7 days, with the following exceptions for treatment-related laboratory abnormalities, uveitis, pneumonitis, bronchospasm, diarrhea, colitis, neurologic toxicity, hypersensitivity reactions, and infusion reactions:

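### Section 9.1.1 counts death as a PFS event, then censors everyone without progression and does not limit that to patients who are alive

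*Combined protocol and SAP*

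**What the plan says.** Section 9.1.1 (Primary Endpoint) defines the endpoint as "progression-free survival (PFS) measured from study entry until documented progression or death from any cause". The sentence that follows is the section's only censoring rule for the primary analysis: "Patients who have not experienced progression will be censored at the date of the last radiographic assessment". It does not mention patients who have died.

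The section sets 35 patients against a historical median of 5.5 months, with a target of 7.3 months (hazard ratio 0.75), 80% power and a one-sided alpha of 0.2 for a test of a single exponential mean. It expects 32 PFS events under the alternative.

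On patients who leave treatment, Section 9.1.1 says: "These patients will be followed for PFS, even if they are removed from treatment due to unacceptable toxicity or because they withdrew consent". Section 5.7 (Subject Discontinuation) treats two acts as separate: "subjects may discontinue study treatment or withdraw their consent to participate in the study at any time without prejudice".

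**The concern.** Take a patient scanned at week 9 without progression who dies at week 17, before the next scan. By the definition this is an event at week 17. By the censoring sentence the patient has not progressed and leaves the analysis at week 9 as a censored observation. Both are stated rules for the primary endpoint, and nothing else in the combined protocol and SAP says which prevails.

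Death before documented progression is closely tied to prognosis, so censoring it is informative. The trial has one arm and a fixed historical benchmark, so no concurrent control would carry the same error and cancel it.

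A smaller ambiguity sits in the same section. It promises PFS follow-up after consent is withdrawn but does not say whether consent to treatment or consent to the study is meant.

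**Working it through.** **Inputs.** From Section 9.1.1: medians of 5.5 and 7.3 months, hazard ratio 0.75, 35 patients, 32 expected events, one-sided alpha 0.2. From Sections 5.2 and 5.6: scans every 9 weeks. Assumed, because the documents do not give it: the share q of PFS events that are deaths without documented progression, taken as 5%, 10% and 20%.

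**The plan's own figure.** For a test of a single exponential mean with d events, power = P(χ² on 2d df > HR × c), where c is the 80th percentile of χ² on 2d df.

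- d = 35: c = 79.71; 0.75 × 79.71 = 59.79 (before rounding of c); power 0.803.
- d = 32: c = 73.28; 0.75 × 73.28 = 54.96; power 0.783.

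The stated 80% is reproduced to within 2 percentage points.

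**Shift in the median under the literal censoring sentence.** With a constant hazard, removing a share q of events leaves a hazard of (1 − q) times the PFS hazard, so the median tends to 5.5/(1 − q):

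- q = 5%: 5.5/0.95 = 5.79 months
- q = 10%: 5.5/0.90 = 6.11 months
- q = 20%: 5.5/0.80 = 6.88 months

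This formula treats deaths as censored when they occur. A simulation with 9-week scans, which moves the censoring back to the last scan, gave 5.72, 6.03 and 6.70 months. Hence the ranges 5.7–5.8, 6.0–6.1 and 6.7–6.9. At q = 10% the formula gives a spurious gain of 6.11 − 5.5 = 0.61 months, or 0.61/1.8 = 34% of the targeted gain of 7.3 − 5.5 = 1.8 months.

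**Events lost.** 32 × (1 − q) = 30.4, 28.8 and 25.6, or about 30, 29 and 26.

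**Type I error when the true median is 5.5 months.** The test rejects when χ²/(1 − q) exceeds c, so the error is P(χ² on 2d df > (1 − q) × c), with d the reduced event count:

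| q | d | c | (1 − q) × c | type I error |
|---|---|---|---|---|
| 5% | 30 | 68.97 | 65.52 | 0.29 |
| 10% | 29 | 66.82 | 60.13 | 0.40 |
| 20% | 26 | 60.33 | 48.27 | 0.62 |

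The nominal value is 0.20. These figures start from the 32 events expected under the alternative and censor at death. Censoring at the earlier last scan would lower them slightly.

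**Direction.** The bias is usually upward, but not in every data set. Suppose patient A is last scanned at week 9 and dies at week 17, B progresses at week 12 and C at week 27. With A's death as an event, the Kaplan-Meier estimate just after week 12 is 2/3. With A censored at week 9, only B and C are at risk at week 12, and it is 1/2.

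**The case against.** The strongest reply is that a censoring rule applies only to patients without an event, and the sentence just before it makes death an event. On that view the second sentence merely leaves out a few words, and any experienced programmer would supply them. Much of this stands. A reader might infer that the plan sets out to censor deaths and that PFS is therefore overstated. The documents do not support that: the definition says the opposite, and the numerical effect depends on the literal reading and on an assumed q. The primary objective is also worded as describing PFS.

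It does not remove the conflict. The censoring sentence is the only such rule for the primary analysis, its words cover a patient who has died, and the trial was sized as a test against 5.5 months.

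On consent, the phrase concerns patients removed from treatment. Section 5.7 lists withdrawn consent among the reasons for discontinuation, and Section 5.3 provides disease follow-up off treatment. The text can therefore be read as withdrawal from treatment with follow-up continuing. That is a fair reading, so this part is a request for clarity. It has no shown effect on PFS.

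A reader might also infer that the section credits unscanned time as progression-free. The primary rule does not, because it censors at the last scan. Only the labelled secondary analysis ("As a secondary analysis, these patients will be censored at the time they were removed from treatment") uses the removal date. In simulation, with removal unrelated to prognosis and affecting 10–30% of patients, that rule gave a median of 7.3 months against a true 7.3. Last-scan censoring gave 7.0–7.2. There is no case here for changing the secondary analysis.

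**Conclusion.** The first two sentences of Section 9.1.1 conflict for any patient who dies without documented progression, and this should be corrected before the primary analysis is programmed. The event definition is sound; the censoring sentence is wrong as written because it lacks a restriction to living patients.

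Overstatement of PFS is conditional. It arises only if that sentence is applied literally. It is the usual direction, not an invariable one, and its size depends on q. Over the assumed range of 5% to 20% the effect on both the median and the type I error is material. If deaths are counted as the definition says, the stated design is unchanged.

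**What to change.** Replace the censoring sentence with: *Patients alive without documented progression are censored at the date of the last radiographic assessment; death without documented progression is an event at the date of death.*

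In the same edit, state that PFS follow-up after withdrawn consent applies to patients who withdraw from treatment but still consent to follow-up, in line with the distinction in Section 5.7. Leave the secondary analysis as it is.

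The cost is one replaced sentence and one clarifying clause. No new data are needed, since Section 5.3 already provides survival follow-up, and the sample size and power statement do not change. If the literal rule had been the one programmed, the PFS estimate would usually become less favourable.

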2.0 OBJECTIVES

2.1 Primary Objective

The primary objective of this trial is:

1. To describe the progression free survival (PFS) associated with the combination of pembrolizumab, oxaliplatin and capecitabine (pembro+XELOX) in all patients with previously untreated metastatic esophagogastric adenocarcinoma.

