9.1.3 Exploratory Endpoints

CD8 and PDL1 staining measured by IHC are the primary biomarker endpoints for this study. Descriptive statistics will be provided for each of these endpoints at each time point (pre-, P, and on-treatment, OT) and for the change P vs OT.

For continuous CD8 and PDL1 expression measures (e.g., percentages), the paired t-test will be used to compare change in P vs OT. We expect approximately 25 patients to have paired measurements. With 25 patients studied a difference of 0.53 standard deviation (SD) can be detected with 90% power (1-sided $\alpha=0.1$). With this sample size differences of 13%, 27%, and 40% can be detected with 80% power assuming SDs of 0.25, 0.5, and 0.75, respectively.

For dichotomous paired proportions (e.g., <2+ versus >2+ by IHC) McNemar's test will be used to test the null hypothesis that the difference in P and OT proportions is 0 versus the alternative that it is > 0 or < 0. With 25 paired patient samples studied 79% power is achieved to detect the difference illustrated in Table 1a below and 86% power is achieved to detect the difference illustrated in Table 1b (2-sided $\alpha=0.1$).

Table 1a: Alternative hypothesis resulting in 79% power using McNemar's test (2-sided $\alpha=0.1$).

	Post Treatment		Total
Pre Treatment	<2+	>2+	
<2+	0.15	0.45	0.60
>2+	0.10	0.30	0.40
Total	0.25	0.75	1.00

Table 1b. Alternative hypothesis resulting in 86% power using McNemar's test (2-sided $\alpha=0.1$).

	Post Treatment		Total
Pre Treatment	<2+	>2+	
<2+	0.10	0.50	0.60
>2+	0.10	0.30	0.40
Total	0.20	0.80	1.00

Similar analyses will be conducted for other biomarkers as described in Section 8.0. No adjustments will be made for multiple comparisons. Data transformations or non-parametric methods will be used as appropriate.

Associations between changes in immune infiltrates and outcomes (PFS, RR, OS) will be explored using Cox regression (PFS), 2-sample t-tests or non-parametric Wilcoxon rank-sum tests, or the Chi-square test (6-month PFS, RR) based on the distribution and structure of the data (i.e., either parametric or non-parametric methods will be used as appropriate).

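### Does the 80% power behind the 35 patients belong to a PFS test that the primary analysis never says it will run?

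*Combined protocol and SAP*

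**What the plan says.** The primary objective (section 2.1) is "To describe the progression free survival (PFS) associated with the combination of pembrolizumab, oxaliplatin and capecitabine". Section 9.1.1 then takes a historical benchmark, "a median PFS of approximately 5.5 months is expected for patients treated with oxaliplatin and capecitabine alone", and supports the sample size with a power statement: "With 35 patients enrolled, the difference between a historical median PFS of 5.5 months and experimental median of 7.3 months", stated as a hazard ratio of 0.75, "can be detected with 80% power (1-sided test of single exponential mean", at alpha 0.2).

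The next paragraph turns to estimation: "PFS and median PFS will be estimated using the Kaplan-Meier method", and "The 95% confidence interval estimate for median PFS will be computed using the variance estimate proposed by Brookmeyer and Crowley". It closes with "Under the alternative hypothesis, 32 PFS events are expected at the end of the follow-up period". The section goes on to define who is followed for PFS and a secondary analysis that censors at removal from treatment. It does not say that the exponential test will be carried out, does not give a critical value, and does not say how the interval is to be read against 5.5 months. No other section supplies such a rule.

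**The concern.** Power is a property of a particular test. Here it belongs to a parametric test at one-sided alpha 0.20, while the reported analysis is a nonparametric median with a two-sided 95% interval. The contrast with section 9.1.3 sharpens the doubt: for the exploratory markers the plan says outright that "the paired t-test will be used to compare change in P vs OT", and it gives power for that test. Only the primary endpoint has a powered test with no matching instruction to run it.

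At stake is how the result would be read. In a single-arm trial judged against a historical median, the same data could be called promising or inconclusive depending on the yardstick. A reader who asked the 95% interval to exclude 5.5 months would be using a far stricter standard than the one that sized the trial, and a true median of 7.3 months would usually fail it.

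**Working it through.** **Inputs (section 9.1.1 unless noted).** n = 35; null median 5.5 months; alternative 7.3 months, given as hazard ratio 0.75 (5.5/7.3 = 0.7534); one-sided alpha 0.20; 32 expected events. The synopsis gives 12 months' accrual and study completion 3 years after the last subject starts.

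**1. The plan's own power.** With d events and exponential times, 2d × (estimated mean)/(true mean) follows a chi-square distribution on 2d degrees of freedom. Hence power = P(χ²(2d) > HR × q), where q is the 80th percentile of χ²(2d).

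| Events d | q | Power, HR 0.75 | Power, HR 5.5/7.3 |
|---|---|---|---|
| 32 | 73.276 | P(χ²(64) > 54.957) = 78.3% | P(χ²(64) > 55.208) = 77.5% |
| 34 | 77.571 | 79.6% | 78.9% |
| 35 | 79.715 | P(χ²(70) > 59.786) = 80.3% | 79.6% |

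The normal approximation agrees: Φ(√35 × 0.2877 − 0.8416) = Φ(0.860) = 80.5% at 35 events and HR 0.75. The stated 80% reproduces, most closely if all 35 patients have an event. At 32 events the shortfall is about two percentage points.

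**2. Are 32 to 35 events plausible?** With λ = ln 2/7.3 = 0.09495 per month, uniform 12-month accrual, minimum follow-up F and no other loss, expected events are 35 × {1 − [exp(−λF) − exp(−λ(F+12))]/(12λ)}. This gives 31.2 at F = 18, 32.9 at F = 24 and 34.3 at F = 36 months. The plan's 32 is in line with this once some loss is allowed for.

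**3. Can the rule be recovered?** Reject when the exponential estimate of the median exceeds 5.5 × q/(2d). At 32 events this is 5.5 × 73.276/64 = 6.30 months; at 35 it is 5.5 × 79.715/70 = 6.26 months. Equivalently, the one-sided 80% lower bound must exceed 5.5 months. Every input is in section 9.1.1, and no further choice is required. Simulated under the plan's accrual and follow-up, this rule has type I error 0.20 and power 0.80 without dropout. With an assumed dropout of 0.8% per month (about 32 events), power is 0.78.

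**4. Where the low figures come from.** Suppose instead that the 95% Kaplan-Meier interval had to exclude 5.5 months. Under the alternative, the chance of being event-free at 5.5 months is 0.5^(5.5/7.3) = 0.593. Without early censoring, the lower limit exceeds 5.5 months when at least 24 of 35 patients are event-free then (plain or log-log interval), with probability 17%. For a log interval the requirement is at least 23 of 35, with probability 28%. The corresponding error rates at a true 5.5 months are about 2% and 4.5%. Much of the drop is the stricter level: the exponential test itself at one-sided 0.025 has 40% to 42% power at 32 to 34 events (HR 5.5/7.3).

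These figures also assume that progression is observed exactly when it occurs. Scans are every 9 weeks. A crude version that moves each event to the next scan gave 48% to 68%, with type I error of 15% to 30%. So the figures for this rule depend heavily on assumptions outside the plan.

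**5. Other support for 35.** Section 9.1.2 also ties 35 patients to precision of the response rate: 1.645 × √(0.25/35) = 0.139, matching its ± 0.14. The PFS power statement is therefore not the sole basis for the sample size.

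**The case for a change.** The strongest case for a change is that a rule which can be inferred has not been prespecified. In a single-arm comparison with a historical figure, the success criterion is the thing to settle before the data are seen. At least three readings are open: the exponential test at 0.20 (about 78% power), exclusion of 5.5 months by the 95% interval (17% to 28%), and a bare observed median above 5.5 months (about 50% type I error, 87% power). The authors name their tests explicitly for exploratory markers, and two or three sentences would settle the matter.

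Part of this stands. The plan never says that the test will be run, and an explicit sentence would be better drafting.

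The rest carries less weight. The three readings do not have equal standing in the text: only the first has its null, alpha, direction and alternative written down. The other two are rules a reader would have to supply. The hypothesis framework is not abandoned in the analysis paragraph either, since that paragraph counts the events expected under the alternative. The absence of a phrase used in section 9.1.3 does not show that the test was dropped. Reporting a median and interval beside a test used for sizing is ordinary in a phase II trial whose objective is descriptive. Whether to add a formal test or to recast the sample size in terms of precision is a choice on which statisticians could reasonably differ.

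**Conclusion.** The observation is accurate, but it is a gap in the drafting and not a defect in the design. The power claim holds to within about two percentage points: 77.5% to 78.3% at 32 events, and 79.6% to 80.3% at 35. Anyone wanting the implied decision can derive it from section 9.1.1 alone (exponential median estimate above about 6.30 months at 32 events). Anyone following the analysis text as written obtains a valid Kaplan-Meier median and interval, which is what the objective asks for. Neither the sample size nor any estimate would change.

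This rests on exponential PFS times, on about 32 to 35 events being observed, and on the 95% interval being read as a description of precision. The power of a rule that the interval must exclude 5.5 months should not be presented as a property of this plan. If the section is revised for other reasons, a sentence saying whether the named test will be reported, and labelling the interval descriptive, would be a courtesy to readers.
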